#### 4.1 **Selection of Study Population**

Patients will be included from Medical Intensive Care units and regular wards at Oslo University Hospital, Norway, but may be extended to other wards at OUS or nearby hospitals to ensure an adequate number of both categories of participants.

The patients will be identified by screening of hospital records by the study staff and invited to participate and informed about the study by the study staff after consultation with the treating physician. If deemed necessary to include an adequate number of patients with existing samples in existing bio banks, prospective participants may also be screened by querying the bio bank (Janus) for information about existing samples from the prospective participant.

#### **Number of Patients** 4.2

58 patients

#### 4.3 **Inclusion Criteria**

- 1. Adults > 18 years old, admitted to hospital with tissue damage, can be included when they are considered medically stable though still expected to remain hospitalized for at least 7 more days (from inclusion).
- 2. Preferably: Previously included in the Janus Cohort or any other cohort or study with stored biological samples.

#### 4.4 **Exclusion criteria**

- Exclusion Criteria 1. Allergy to NR or ingredients in capsules or placebo.
  - 2. Patients expected to pass away within 90 days.
  - 3. Patients unable to give their consent
  - 4. Unstable patients:

- i. Uncontrolled infection (clinical septicaemia, inadequate response to treatment, inadequate control of source of infection or at treating physician's discretion).
- ii. MAP < 70 mm Hg and symptoms of hypotension.
- iii. Patients requiring dialysis at the time of inclusion or GFR <25
- iv. Liver failure with Child-Pugh class B or C or any class associated with hepatic encephalopathy (any grade), ALT or AST >3 times upper limit. If liver transaminases are elevated for other reasons than hepatocyte damage, patients may be included regardless of ALT/AST values \*
- v. Severe peripheral oedema and/or pulmonary oedema, any unstable cardiac rhythm, ongoing myocardial ischemia, troponin T >500.
- vi. Signs of elevated intracranial pressure (headache, vomiting and depressed global consciousness in conjunction with focal neurological signs, papilledema, spontaneous periorbital bruising and a triad of bradycardia, respiratory depression and hypertension).
- vii. Arterial pH <7.30 or >7.50
- viii. Serum potassium under 3, 2 or over 5 mmol/L.
- 5. Pregnancy or breastfeeding \*\*
- 6. Any cancer not in full remission for >10 years (for non-melanoma skin cancers, full remission for >1 year)
- 7. Use of St John's Wort based supplements during the past 30 days
- 8. Patient has undergone solid organ transplantation
- 9. Participation in any clinical trial with unknown medications
- 10. Major gastrointestinal or other major internal bleeding past 2 days.
- 11. Logistical challenges after discharge. Patient must be able to attend follow up.
- 12. Intracerebral haemorrhage or major stroke past week.
- 13. The treating physician considers the patient unfit or unable to participate.
- \*Please also see Amendment number 1.
- \*\* All fertile women must have an HCG test.

#### 5 TREATMENT

Patients will be receiving either NR or placebo.

#### 5.1 Identity, Supply and Storage

NR, in the shape of Tru Niagen (ChromaDex, Inc.) will be used in this study. Both Niagen and placebo capsules can be stored for up to 1 year at room temperature. A 3-month supply of the appropriate dose of either placebo or NR capsules will be packaged into kits by persons that are otherwise not involved in the study (presumably medical students recruited by the study staff). In addition to the required information, the boxes will be marked with dose, administration guidelines and an identification number. The link between the ID number and the content of each box (placebo or NR) will only be known by persons involved in this step. Please see 5.9 "Drug labelling" for more information.

#### 5.2 Dosage and Administration

The capsules are taken orally and contain 250 mg of NR or placebo. Placebo or NR capsules will be administered after randomization as described below. (Please also see flow chart under point 5).

- First 16 patients enrolled: 1 capsule 250 mg every morning.
- Following 16 patients enrolled: 1 capsule of 250 mg morning and evening for three months.

- Following 26 patients enrolled: 2 capsules of 250 mg morning and evening for three months.
- High dose of 1000 mg morning and evening has now been cancelled (12.06.2023)

During hospitalizations the capsules will be administered by the hospital personnel while the capsules will be self-administered after discharge. Three months of NR or placebo will be released to the patient at randomization.

The capsules should ideally be swallowed whole, but if necessary, they may be opened before administration and the content poured into a small amount of water for administration in PEG/nasogastric tube. The content should not be chewed or crushed. The absorption of True Niagen remains the same if administered in this fashion, but unusual administration methods will be registered. The capsules may be opened by the hospital staff, but not by the study staff.

Due to strict inclusion criteria, and the expected frailty level of such patients, it is unlikely that two included patients will meet. It is thus unlikely that opening the capsules will lead to patient un-blinding.

A missed dose should be taken as soon as possible, but not any later than 6 hours after the usual time. If more than 6 hours have passed, the patient should wait until the next dose is scheduled.

#### 5.3 Premedication and Monitoring

No pre-medication will be used. After administration of the first capsule, clinical status shall be monitored every half hour for the first three hours. In case of suspected adverse events, or at the discretion of the treating physician, administration of the study drug can be postponed and this will be recorded in the CRF. In this case the patient will continue to use the medication until all three months' worth of capsules is consumed.

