| Adverse events                       |                     | 1-7, DC  | Χ  | Χ   | Χ                                      | X                   | X                      |
| Survival assessment                  |                     | 1-7, DC  | Х  | Х   | Х                                      | Х                   | х                      |

(DC: Discharge)

\*\*Selected number of patients only

i] And every 7th day onwards if still hospitalized.

ii] All ICU patients and patients on the following medical wards are screened: Infectious diseases, internal medicine, pulmonary medicine and acute medicine. See also own section on screening.

iii] Antibiotics and vitamin B3 containing drugs only.

iv] Full physical examination of all major organ systems.

v] Blood pressure, pulse, temperature, respiration rate and 02 saturation.

[vi] See table 3 below for details.

Table 3: Overview of scoring forms and other assessment methods  $^{**}$ 

| CLINICAL TEST/scoring systems                                    | TIMING  |
|--|---|
|  |   |
| EQ5D (filled in by investigator in the presence of the           | 2 weeks prior to admission. On day 1 and on day 90.                     |
| patient).  |   |
|  |   |
| MOCA   | Day 7 and 90 and week 65.   |
| Trail making A   | Day 7 and 90 and week 65.   |
| Trail making B   | Day 7 and 90 and week 65.   |
| Forward and Backward Recall.                                     | Day 7 and 90 and week 65.   |
| NEWS (completed by nursing staff as part of standard treatment). | - Baseline morning and afternoon, day 3 and day 7.                      |
|  |   |
|  |   |
|  |   |
| 4 meter walking test   | At baseline, day 7, day 90 and week 65.                                 |
| Clinical Frailty score (filled in by investigator)               | Pre-baseline, baseline, day 7, day 90 and week 65.                      |
| Grip strength  | At baseline, day 7, at discharge, day 90 and week 65.                   |
|  | (and every occation at hospital).                                       |
| RASS (completed by nursing staff as part of standard             | Day 0, 1, 3, 7 and every 7 th day thereafter for the         |
| treatment of sedated patients).                                  | duration of stay in ICU   |
|  |   |
| Charlson comorbidity index (Filled in by investigator)           | Baseline  |

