#### 6.2.3 End of Treatment Visit

An end-of-treatment visit will be carried out during the last week of treatment. For logistical reasons, and because potential effects of NR are assumed to be established prior to 90 days, we will allow for a window of 90 days +/- 7 days. Please see 5.1 for details.

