#### 8.4 Time Period for Reporting AE and SAE

For each patient the standard time period for collecting and recording AE and SAEs will begin at day 1 when the first capsule is administered and will continue until 30 days after the end of study visits at day 90. Patients will be asked about side effects, and specifically flushing, at all points of contact with the investigator.

During the course of the study all AEs and SAEs will be proactively followed up for each patient; events should be followed up to resolution, unless the event is considered by the investigator to be unlikely to resolve due to the underlying disease. Every effort should be made to obtain a resolution for all events, even if the events continue after discontinuation/study completion.

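### After a pause, dosing can run past day 90 with no stated limit, while standard adverse-event recording stays tied to the day-90 visit, so a long pause can shorten recording after the last capsule

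*Protocol*

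**What the plan says.** Protocol 5.3 provides that, for a suspected adverse event or at the treating physician's discretion, "administration of the study drug can be postponed and this will be recorded in the CRF". It continues: "In this case the patient will continue to use the medication until all three months' worth of capsules is consumed". No maximum pause is given there. Sections 5.6 (collection of leftovers) and 6.2.6 (reasons for discontinuation) do not supply one either.

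Protocol 8.4 starts standard AE/SAE recording at the first capsule and says that it "will continue until 30 days after the end of study visits at day 90". The clock therefore runs from a visit.

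The timing of that visit is given in several ways:
- Protocol 6.2.3: "An end-of-treatment visit will be carried out during the last week of treatment", and for logistical reasons "we will allow for a window of 90 days +/- 7 days".
- Protocol Tables 1 and 2: day 90 with 10 days either side.
- SAP 2.7: day 90 with 30 days before and 90 days after.

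Table 2 also marks the row for dispensing and returning treatment at the day-90 visit, and Protocol 5.5 asks patients to bring unused tablets to the end of study visit. Section 8.4 uses that visit name for day 90, whereas Table 2 uses it for about week 65.

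**The concern.** The rule for dosing and the rule for recording have different anchors. Dosing after a pause ends when the capsules run out. Standard recording ends at a fixed interval after a visit planned around day 90. Each day of pause moves the last capsule one day later. The close of recording moves only if the visit moves, and the visit has a window.

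At stake is the length of planned observation after the last dose in patients who were paused and restarted. Some of them will have been paused for a suspected reaction, and late observation after re-exposure is most informative in such patients. A new, mild event at home shortly after the last capsules is the kind most likely to be missed or reported late. The concern is confined to safety recording. It does not touch the primary endpoint or the sample size.

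**Working it through.** The documents state no length of recording after the last dose, so there is no figure to reproduce. The check is timeline arithmetic.

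**Inputs**
- Planned treatment of 90 days (Protocol 1.4), taken as a 90-day supply. This is an assumption, because other sections say three months.
- p = total pause in days after the first capsule, unknown.
- V = day of the day-90 visit. Allowed range: 83 to 97 (6.2.3), 80 to 100 (Tables 1 and 2), 60 to 180 (SAP 2.7).
- Standard recording closes 30 days after V (8.4).

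**Formulas**
- Last capsule: L = 90 + p
- Close of standard recording: E = V + 30
- Recording after the last capsule: C = E - L = V - 60 - p

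**Results: C in days, by pause and visit day**

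| p | L | V = 90 | V = 97 (latest, 6.2.3) | V = 100 (latest, Table 2) | V = 180 (latest, SAP 2.7) |
|---|---|---|---|---|---|
| 0 | 90 | 30 | 37 | 40 | 120 |
| 7 | 97 | 23 | 30 | 33 | 113 |
| 10 | 100 | 20 | 27 | 30 | 110 |
| 14 | 104 | 16 | 23 | 26 | 106 |
| 21 | 111 | 9 | 16 | 19 | 99 |
| 28 | 118 | 2 | 9 | 12 | 92 |

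1. *Unpaused patients (p = 0).* C = V - 60, so C ranges from 23 to 37 days (6.2.3), 20 to 40 (Table 2), or 0 to 120 (SAP 2.7).
2. *Keeping a full 30 days.* V - 60 - p >= 30 requires p <= V - 90. With a day-90 visit any pause shortens recording. With the latest visit the limit is 7 days (6.2.3), 10 days (Table 2) or 90 days (SAP 2.7).
3. *Falling below the unpaused minimum.* With the latest visit: 37 - p < 23 gives p > 14 (6.2.3), and 40 - p < 20 gives p > 20 (Table 2). With a day-90 visit: 30 - p < 23 gives p > 7, and 30 - p < 20 gives p > 10. Under SAP 2.7 with the latest visit: 120 - p < 0 gives p > 120.
4. *Dosing outlasting standard recording (C < 0).* p > 30 (day 90), p > 37 (day 97), p > 40 (day 100), p > 120 (day 180).
5. *Sensitivity to supply.* With 92 days of capsules, C = V - 62 - p. The latest-visit limits in step 2 drop by two, to 5, 8 and 88 days. Those in step 3 for 6.2.3 and Table 2 do not change, because paused and unpaused patients lose the same two days.

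**The case against.** The strongest reply is that other text may prevent the gap or make it harmless.

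- *The SAP window is wide.* Under SAP 2.7 a visit as late as day 180 would keep 30 days of recording for pauses up to 90 days. This stands as a limit on the arithmetic. But the same window conflicts with both protocol windows, and its early edge (day 60) leaves an unpaused patient 60 - 60 = 0 days. It does not secure any post-dose period.
- *Capsules may be collected at day 90.* If Table 2 and 5.5 are applied that way, dosing stops at the visit and 30 days of recording follow. This also stands, but then the instruction in 5.3 is not carried out.
- *The visit follows treatment.* Section 6.2.3 places it in the last week of dosing, so it may shift with a short pause. The same section limits the shift to 7 days, and 8.4 names day 90.
- *Adverse events are captured elsewhere.* Section 8.4 says: "Patients will be asked about side effects, and specifically flushing, at all points of contact with the investigator". Table 2 marks "Adverse events" at about week 65 and in follow-up. SAP 7.1 also takes events from hospital records and patient-initiated contact, and its definition of a treatment-emergent event has no end date. Section 6.2.2 expects reactions mainly in hospital. All of this reduces the consequence. What remains is timeliness: week 65 is about day 65 x 7 = 455, some 455 - 120 = 335 days after nominal day 120, whereas 8.7.1 expects the safety committee to hear of an SAE within 4 days. The rule "Every effort should be made to obtain a resolution for all events, even if the events continue after discontinuation/study completion" covers events already known and does not find new ones.
- *It is a preference, and late.* No fixed period after the last dose is promised, and unpaused patients already vary. SAP 7.1 describes AE collection in the past tense, so an amendment may change little in this trial. That is fair, and it is why the point is graded as a small improvement.

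**Conclusion.** The point holds as a minor gap in safety recording. Section 5.3 puts no limit on the pause, 8.4 counts from the visit, and no text links the two. Under the protocol windows, with the visit as late as allowed, a paused patient gets less recording after the last capsule than any unpaused patient seen within the window only if the pause exceeds 14 days (6.2.3) or 20 days (Table 2). This rests on a 90-day supply, on 5.3 being followed past day 90, and on the protocol windows rather than the one in SAP 2.7.

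Two stronger readings are tempting and are not supported. A reader might infer that every pause beyond two or three weeks necessarily cuts observation short. The figure depends on the visit day, on which of three windows applies and on whether capsules are collected at day 90. Against a nominal 30 days the shortening can begin on the first paused day, or not until after 90 days. A reader might also infer that events are lost or that the safety tables are biased. The documents give neither the number nor the length of pauses, several other routes of capture remain open, and no endpoint, analysis set or TEAE table is shown to change.

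**What to change.** In Protocol 8.4, run AE/SAE recording to the later of 30 days after the day-90 visit and 30 days after the last capsule, and add the last-capsule date to the eCRF. This guarantees at least 30 days after the last dose under any of the three windows. In 5.3 and Table 2, state that capsules are not collected at day 90 from a paused patient who is still dosing.

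The cost is a few sentences and one date field. Postponement is already entered in the CRF (5.3), and the timing of treatment changes is already kept in the medical records (9.2). The downside is one later AE phone contact for each patient who resumes after a pause. Recording would also close somewhat later for an unpaused patient seen early in the window.

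If dosing is already complete, list the paused patients in the study report with the actual recording time after their last capsule.

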#### 5.4 Concomitant Medication

The following medication is not allowed while the patient is included in the study:

St Johns Worth

The use of antibiotics, the specific use of aminoglycosides, and use of vitamin B3 containing drugs will be recorded in the patient's file and CRF.

#### 5.5 Subject Compliance

Compliance will be ensured by administration of the study intervention as part of the normal hospital routine while the patients are hospitalized. After hospitalization compliance at home will be ensured by regular contact with the study staff including the end of study interview and a phone call one-month post inclusion to remind patients to take tablets. Patients will also be encouraged to buy a pill organizer and unused tablets and packaging should be brought to the end of study visit for control. The study staff will also ensure administration of the study drug while the patients are at long term care facilities, rehabilitation institutions or under the formal care of other caregivers. Every effort will be made to ensure that the study drug is mentioned in the discharge letter under the section "new medications". This list of medications is routinely circulated to patients, caretakers and the patient's general practitioner.

Finally, compliance will be ensured by measuring mononuclear white blood cell NAD+ levels which are known to be affected by the study drug. These data will be sent from the laboratory to the safety committee and not included in the database before after un-blinding.

#### 5.6 Accountability

One batch containing three months of NR will be distributed to each participant. This batch will be kept and used by the hospital ward during hospitalization and then released to the participant at discharge. Any remaining medication will be collected and counted at the end of study or if a participant withdraws prior to this. Left over medication is to be disposed of in the risk waste boxes for incineration in accordance to the hospital policy.

#### 5.7 Labelling

NR 'a 250 mg and placebo will have a label permanently affixed to the outside of the container. Labelling will be in accordance with ICH, GCP and national regulations, and will clearly state that the material is for clinical trial / investigational use only and that it should be kept out of reach of children.

#### Label:

Information on the labels is printed in Norwegian. It's English translation follows:

#### Investigating product or placebo

Contains: 250 mg nicotinamide riboside capsules or placebo.

Batch number. Expiration date.

Dosage: Corresponds to the phase of the study, please see 4.2

For clinical investigation only.

To be kept refrigerated or in room temperature.

Keep away from children.

The capsules can be swallowed or opened and the content poured into water.

Patient inclusion number.

Patient's initials.

Protocol code

Date dispensed

Name of prescribing doctor

The sponsor of this study is: Oslo Universitetssykehus, Avdeling for molekylær mikrobiologi, [name]

Contact persons: Medical doctor [name] (mobil: [name]) or Principal investigator [name] (mobil: [name]).

#### Studiepreparat for B3Short studien eller placebo.

Innehold: 1 kapsel inneholder 250 mg nikotinamide riboside eller placebo

Batch nummer:

Utløpsdato:

Dosering

Til klinisk utprøvning.

Oppbevares i romtemperatur eller kjøleskap.

Oppbevares utilgjengelig for barn.

Kapslene svelges hele el åpnes og innholdet løses opp i vann og drikkes.

Pasientens inklusjonsnummer:

Pasientinitialer:

Protokollnummer: [name]

Startdato:

Utskrivende lege:

**Studiesponsor:** OUS, Avd. for Molekulær Mikrobiologi, [name]. **Kontaktpersoner:** [name] (tlf [name]), [name] (tlf [name]).

Empty lines to be filled in during packaging (Batch number, expiration date and dose, patient's inclusion number) or by the investigator at inclusion (patient's initials, starting date and prescribing doctor).

#### 5.8 Subject Numbering

Each subject is identified in the study by a unique subject number that is assigned when subject signs the Informed Consent Form and takes the first capsule. Once assigned the subject number cannot be reused for any other subject. The first patient included in the study will be included in phase 1 and thus receive the ID number 101, the second patient 102 and so on. The first patients enrolled in the following phases will hence be subject number 201, 301 and so forth.

## **6 STUDY PROCEDURES**

## 6.1 Timing of investigations

Table 1: Timing of laboratory tests and biobanking

|                     |        | Inpatients |            |        |                  | Outpatients     |                    |
|---------------------|--------|------------|------------|--------|------------------|-----------------|--------------------|
|                     | Day 1* | Day 3 +/-1 | Day 7 +/-1 | Weekly | Day 90 +/-
10 | Withdrawl visit | Week 65
and 150 |
| Na                  | X      | X          | Χ          | Χ      | Χ                | Χ               | Χ                  |
| K                   | X      | Χ          | Χ          | Χ      | Χ                | X               | Χ                  |
| Calcium             | X      | Χ          | Χ          | Χ      | Χ                | X               | Χ                  |
| Mg                  | X      | Χ          | Χ          | Χ      | Χ                | Χ               | Χ                  |
| Phosphate           | X      | Χ          | X          | Χ      | Χ                | X               | Χ                  |
| Urea                | X      | Χ          | Χ          | Χ      | Χ                | Χ               | Χ                  |
| Creatinin           | X      | Χ          | Χ          | Χ      | Χ                | X               | Χ                  |
| GFR                 | X      | Χ          | Χ          | Χ      | Χ                | X               | Χ                  |
| Albumin             | X      | Χ          | X          | Χ      | Χ                | Χ               | Χ                  |
| Bilirubin           | X      | Χ          | Χ          | Χ      | Χ                | Χ               | X                  |
| CRP                 | X      | X          | Χ          | Χ      | X                | Χ               | Χ                  |
| ALP                 | X      | Χ          | Χ          | Χ      | Χ                | Χ               | Χ                  |
| ASAT                | Х      | X          | Χ          | Χ      | Χ                | X               | Χ                  |
| ALAT                | X      | X          | Χ          | Χ      | X                | X               | Χ                  |
| LT                  | X      | Χ          | X          | Χ      | Χ                | Χ               | Χ                  |
| GT                  | X      | X          | Χ          | Χ      | X                | X               | Χ                  |
| Pancreas
amylase | X      | Х          | Χ          | Х      | Х                | X               | Χ                  |
| Uric acid           | x      |            | x          |        | х                | x               | X                  |
| Homocystein         | Х      | Χ          | Χ          | Χ      | Χ                | Χ               | Χ                  |
| Ferritin            | X      | Χ          | Χ          | Χ      | Χ                | Χ               | Χ                  |
| Hb                  | X      | Χ          | Χ          | X      | Χ                | X               | Χ                  |
| Leucocytes          | X      | Χ          | Χ          | Χ      | Χ                | Χ               | Χ                  |
| Trombocytes         | X      | Χ          | X          | X      | Χ                | Χ               | Χ                  |
| INR                 | X      | Χ          | Χ          | Χ      | Χ                | Χ               | Χ                  |
| v-PH                | Х      | Χ          | Χ          | Χ      | Χ                | Χ               | Χ                  |
| v-HCO3              | Х      | X          | Χ          | Χ      | X                | Χ               | Χ                  |
| Pro-BNP             | Х      |            | Χ          | Χ      | X                | Χ               | Х                  |
| Troponin-t          | Х      | Χ          | Χ          | Χ      | Χ                | Χ               | Χ                  |
| CK                  | Х      | X          | Χ          | Χ      | Х                | Χ               | Χ                  |
| HbA1c               | Х      |            |            |        | X                | Χ               | Χ                  |
| гѕн                 | Х      |            | Χ          | Χ      | Х                | Χ               | Χ                  |
| Ft4                 | Х      |            | Χ          | Χ      | Χ                | Χ               | Χ                  |
| Folate              | Х      |            | Χ          | Χ      | Х                | Χ               | Χ                  |
| LDL                 | X      |            | Χ          | Χ      | Χ                | X               | Χ                  |

| HDL                                   | X | Χ | Χ | Χ | Χ | X |
|---------------------------------------|---|---|---|---|---|---|
| Total
Cholesterol                  | X | Х | Х | Х | Х | X |
| BIOBANKING:                           |   |   |   |   |   |   |
| 4x EDTA                               | X | Χ |   | Χ | Χ | Х |
| 1x Serum                              | X | Χ |   | Χ | Χ | Χ |
| 1x Plasma                             | X | X |   | Χ | Χ | X |
| 2x CPT                                | X | Χ |   | Χ | Χ | Χ |
| Urine, faeces, saliva,buccal swabs ** | x | x |   | x | x | х |

\* Prior to administration of intervention drug

Table 2: Timing of inclusion and procedures.

|                                      | Screening
period | Treatment Period At inclusion (1), day 3, 7 [i] And on discharge (DC) | Mid-
treatment
follow-up
phone call | Last week
of
treatment
visit at 90
days+/- 10 | End of
study
visit ca
65 wks. | Withdrawal
visit | Follow
up
period |
|--------------------------------------|---------------------|--|--|---|--|---------------------|------------------------|
| Screen patients [ii]                 | Х                   |  |  |   |  |                     |                        |
| Informed consent                     | Х                   |  |  |   |  |                     |                        |
| Inclusion + exclusion criteria       | Х                   |  |  |   |  |                     |                        |
| Medical history, prior treatment.    | Х                   |  | Х  |   |  |                     |                        |
| Treatment dispensed/returned         |                     | 1  |  | ×   |  | х                   |                        |
| Concomitant medication[iii]          | Х                   | 1-7, DC  | Х  | Х   | Х                                      | Х                   |                        |
| Physical examination [iv]            | Х                   | 1-7  |  | Х   | х                                      | Х                   |                        |
| Vital signs [v]                      | Х                   | 1-7  |  | Χ   | X                                      | Х                   |                        |
| Tests/questionnaires [vi] |                     | 1-7,   |  | Х   | Х                                      | Х                   |                        |
| Adverse events                       |                     | 1-7, DC  | Χ  | Χ   | Χ                                      | X                   | X                      |
| Survival assessment                  |                     | 1-7, DC  | Х  | Х   | Х                                      | Х                   | х                      |

(DC: Discharge)

\*\*Selected number of patients only

i] And every 7th day onwards if still hospitalized.

ii] All ICU patients and patients on the following medical wards are screened: Infectious diseases, internal medicine, pulmonary medicine and acute medicine. See also own section on screening.

iii] Antibiotics and vitamin B3 containing drugs only.

iv] Full physical examination of all major organ systems.

v] Blood pressure, pulse, temperature, respiration rate and 02 saturation.

[vi] See table 3 below for details.

Table 3: Overview of scoring forms and other assessment methods  $^{**}$ 

| CLINICAL TEST/scoring systems                                    | TIMING  |
|--|---|
|  |   |
| EQ5D (filled in by investigator in the presence of the           | 2 weeks prior to admission. On day 1 and on day 90.                     |
| patient).  |   |
|  |   |
| MOCA   | Day 7 and 90 and week 65.   |
| Trail making A   | Day 7 and 90 and week 65.   |
| Trail making B   | Day 7 and 90 and week 65.   |
| Forward and Backward Recall.                                     | Day 7 and 90 and week 65.   |
| NEWS (completed by nursing staff as part of standard treatment). | - Baseline morning and afternoon, day 3 and day 7.                      |
|  |   |
|  |   |
|  |   |
| 4 meter walking test   | At baseline, day 7, day 90 and week 65.                                 |
| Clinical Frailty score (filled in by investigator)               | Pre-baseline, baseline, day 7, day 90 and week 65.                      |
| Grip strength  | At baseline, day 7, at discharge, day 90 and week 65.                   |
|  | (and every occation at hospital).                                       |
| RASS (completed by nursing staff as part of standard             | Day 0, 1, 3, 7 and every 7 th day thereafter for the         |
| treatment of sedated patients).                                  | duration of stay in ICU   |
|  |   |
| Charlson comorbidity index (Filled in by investigator)           | Baseline  |
| Hearing Assessment **  | At baseline, day 7, day 90 and week 65.                                 |
|  |   |
| SAPS2 (Filled in by investigator).                               | On admission to ICU or first day at hospital for patients never at ICU. |

(\*) Portable audiometry, tympanometry and otoscopy.

- 2: EQ5D.
- 3: Forward-backward recall.
- 4: Trailmaking A.
- 5: 4 meter walking test.
- 6: Trailmaking B.
- 7: MOCA
- 8: Hearing assessment.

(\*\*) Patient's level of fitness will vary considerably and individual evaluations will be made for all patients regarding their ability to complete all or some of these assessments. For patients who are capable of competing all individual tests, but for whom the sum of the assessments is too large, the assessments should for the most part be prioritized as follows:1: Grip strength.

